Primary: To estimate the percentage of patients progressing at 6 months by RECIST1.1 when maintained on a combination regimen of paricalcitol plus pembrolizumab versus pembrolizumab alone.

Secondary:

1. Evaluate the toxicity of the combination of paricalcitol plus pembrolizumab versus pembrolizumab alone.
2. Evaluate the difference in overall survival (OS) in patients administered the combination of paricalcitol plus pembrolizumab versus pembrolizumab alone.
3. Define the impact of the combination of paricalcitol and pembrolizumab on tumor mutational landscape and transcriptional programs.
4. Identify cellular VDR targets in the immune microenvironment with PD1 blockade.

Exploratory:

1. Evaluate the difference in disease progression according to iRECIST vs. RECIST 1.1 criteria (Appendix 5)
2. Assess the utility of a Patient Personalized Clinical Benefit (PPCB) phone-based

| |
|---|
| 
application
 
 3. Assess the association between improvement in symptoms as recorded by the Patient Personalized Clinical Benefit (PPCB) with progression at 6 months by RECIST 1.1 4. Assess any changes in tumor and/or tissue texture on imaging in both arms of the trial 5. To monitor and compare the gut microbial communities in both arms of the trial. |
| 
Trial Design: Randomized Double Blind, Placebo Controlled
 |
| 
No. Patients: Total of 24, 12 randomized to each treatment arm
 |
| 
Name, dose of drugs:
 
 • Pembrolizumab (Keytruda®) 200 mg administered as an intravenous infusion over 30 minutes every 3 weeks. • Paricalcitol (Zemlar®) 25 mcg administered intravenously 3 times per week (given on days 1, 3, 5, 8, 10, 12, 15, 17, 19 ± 1 day of each 21 day cycle) and prior to each pembrolizumab infusion. • Placebo- equivalent volume administered intravenously, 3 times per week and prior to each pembrolizumab infusion. |
| 
Treatment Arms: Arm1: pembrolizumab + paricalcitol Arm 2: pembrolizumab + placebo (saline solution)
 |
| 
Patient Population: Patients with stage IV pancreatic cancer who have been put in best response, defined as: Must have obtained a best response of at least stable disease (SD) or partial response (PR) for a period of 2 months with no further shrinkage of ≥ 30% on scan.
 |

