| 
Endpoints: Primary: The percent of patients with radiographic disease progression according to RECIST 1.1 at 6 months. Secondary:
 
 • Incidence of toxicities • Overall survival • Mutational landscape • Transcriptional programs • Cellular (immunity) VDR targets in the immune microenvironment 
Exploratory:
 
 • Difference in disease progression according to RECIST 1.1 and iRECIST (Appendix 5) criteria • Compliance rate responding to a phone - based application for the assessment of patient |

defined symptoms

- Improvement in symptoms as recorded by the Patient Personalized Clinical Benefit (PPCB)
- Differences in tumor and/or tissue texture on CT scans between the two treatment arms
- Differences in gut microbial communities within and between fecal samples using alpha and beta diversity metrics based on 16S rRNA sequencing

Inclusion criteria:

1. Be willing and able to provide written informed consent for the trial.
2. Be ≥ 18 years of age on day of signing informed consent.
3. Histologically or cytologically confirmed pancreatic adenocarcinoma with metastasis, who had obtained a best response of at least stable disease (SD) or a partial response (PR) for a period of 2 months with no further shrinkage of $\geq 30\%$ on scan on their first line of chemotherapy for their advanced metastatic disease. **Note:** *Patients that have had prior chemotherapy as adjuvant or neoadjuvant therapy are permitted.*
4. Have a performance status of 0 or 1 on the ECOG performance scale.
5. Able to submit an archival tumor specimen (primary or metastatic site) and a discussion is documented with trial investigator at screening that patient will consider providing tissue from a newly obtained core or excisional biopsy of a tumor lesion at baseline and a second biopsy 9 weeks after starting trial treatment, unless tumor is considered inaccessible or biopsy is otherwise considered not in the patients' best interest. *Participation in this trial is not contingent on patient consenting to optional tumor biopsies.*
6. Demonstrate adequate organ function as defined in Table 2, AND serum corrected calcium value must be \leq Institutional ULN and ≥ 8.0 mg/dL, and phosphorus levels must be \leq Institutional ULN and ≥ 2.5 mg/dL.
7. Female participants of childbearing potential should have a negative serum pregnancy test within 24 hours prior to receiving first dose of trial medication.

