1.5 Paricalcitol (Zemplar®)

Refer to Appendix 2- Package Insert for Paricalcitol for complete information.

Paricalcitol is a vitamin D analog used for the prevention and treatment of secondary hyperparathyroidism. Excessive amounts of vitamin D compounds including paricalcitol can cause over suppression of the parathyroid hormone, hypercalcemia, hypercalciuria, hyperphosphatemia and adynamic bone disease.

Paricalcitol should not be given to patients with evidence of vitamin D toxicity, hypercalcemia, or hypersensitivity to any ingredient in this product.

The most common side effects of treatment with paricalcitol are diarrhea, nasopharyngitis, dizziness, vomiting, hypertension, hypersensitivity, nausea and edema.

Taste perversion, such as metallic taste, and allergic reactions, such as rash, urticaria and pruritus rarely have been reported.

Risks associated with treatment with paricalcitol include: Symptoms of elevated calcium levels e.g. feeling tired, difficulty in thinking clearly, loss of appetite, nausea, vomiting, constipation, increased thirst, increased urination and weight loss. Prescription based doses of vitamin D should be withheld during treatment with paricalcitol.

The effects of paricalcitol on unborn fetus and possible transmission through breast milk have not been fully established. Patients on paricalcitol should avoid pregnancy and should not breast feed.

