4.3 Randomization or Treatment Allocation

Randomization will be in a 1:1 ratio to pembrolizumab + paricalcitol or pembrolizumab + placebo. Randomization will be performed by the trial biostatistician or designee using a computer-generated algorithm with a block size of 4. The RAND function in MySQL is used to generate a random number, with a value based on the computer clock used as seed. The program randomly assigns participants to one of the two treatments with the pre-selected block size. After study initiation, the randomization sequence will be provided to the unblinded central monitor. After consent and confirmation of eligibility, the site study coordinator will notify the site pharmacist and the unblinded monitor. The unblinded monitor will provide the next randomized treatment from the sequence to the site pharmacist. The unblinded monitor also will notify the trial biostatistician. The trial biostatistician or designee will be available to assist with identifying the next randomized treatment if the unblinded central monitor is not available.

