8.2 Sample Size Considerations

The primary endpoint is the percentage of patients progressing at 6 months. Based on a contemporary control of no maintenance after best response to prior chemotherapy⁸, the control arm with pembrolizumab alone is expected to have only 8% of patients with no progression at 6 months. To be of clinical interest, at least 58% of patients must be progression-free at 6 months on the pembrolizumab plus paricalcitol arm. A sample size of 12 patients per arm will provide 90% statistical power to detect this difference assuming a one-sided alpha level of 0.05. A one-sided test was selected as we are only interested in the combination if it decreases the percentage of patients progressing at 6 months. This sample size estimate was obtained using binomial enumeration of all possible outcomes to compare two independent binomial proportions (Pearson's chi-squared test) using PASS 15.¹⁸ A statistical concern is that the Pearson chi-squared test does not guarantee the alpha level. We confirmed that we have adequate statistical power using the Miettinen & Nurminen¹⁹ exact likelihood score method (89% power) using Pass 15.

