8.3.6.3 Patient Personalized Clinical Benefit

The symptoms identified by each patient and the change across time will be evaluated graphically. The most severe ranking across the three items will be compared at baseline and the EOT visits to determine whether each patient's symptoms have improved across time. The relationship between progression at 6 months by RECIST 1.1 versus the change in rankings from baseline to EOT will be assessed using a Wilcoxon Rank Sum test.

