personal user information is stored in the database. There is no name, email or any other information that is stored in the database that could be used to identify the individual utilizing the application.

ACCESS AND SUPPORT

The link to the app in the Android "Play Store" or Apple "App Store" can be provided via email or directly searched for using the app name. Initial usability support would be provided by the app support staff. An email distribution list will be set up for any support issues. Any technical issues would be emailed to that distribution list with an expected turnaround time of <24 hrs.

When the app is run on either Android or iOS platforms, the only identifiable information that is sent and used to identify the end user is the initial "ID" that is entered to start the app. The user's IP address, phone model, or phone number are not collected by the app.

DATA ANALYSIS

Frequency distributions and descriptive statistics will be computed on all variables. Any continuous variable with a markedly non-normal distribution will be transformed to more closely approximate a normal distribution.

The compliance rate to weekly reporting will be computed as the number of assessments completed divided by the number of expected assessments. Number of questions completed, duration of each reporting session, and time of day of each reporting session will be analyzed using descriptive statistics. Statistical analysis will employ both daily scores for individual items as well as summary measures (e.g., mean scores computed per item per patient over each 8 week period in which at least 4 surveys are completed). Patient weekly and monthly scores for individual items will be graphically displayed longitudinally using stream plots and mean plots. Mean scores with standard deviations will be computed at each time point (weekly as well as monthly). Mean scores for each individual item over time (weekly and monthly) will be modeled using a generalized linear mixed model with a covariate for time (weeks or months since registration) and a random intercept term per patient. Correlations between items will be assessed using Pearson correlations at fixed time points. The threshold for feasibility is estimated at 70%. Finally, coordinator feedback will be collected via interviews and qualitatively analyzed.

REFERENCES

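### No planned PPCB analysis uses randomised arm, so the trial never estimates whether adding paricalcitol changes patient-reported symptoms (minor; exploratory endpoint)

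*Protocol*

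**What the plan says.** The synopsis and Protocol 3.3 give PPCB two exploratory objectives: the utility of the phone application, and to "Assess the association between improvement in symptoms as recorded by the Patient Personalized Clinical Benefit (PPCB) with progression at 6 months by RECIST 1.1". Symptom improvement recorded by PPCB also stands as an exploratory endpoint in its own right in Protocol 3.6. The design is 1:1 and double-blind: "Randomization will be in a 1:1 ratio to pembrolizumab + paricalcitol or pembrolizumab + placebo", with "Total of 24, 12 randomized to each treatment arm".

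The analyses are in two places.

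- **Protocol 8.3.6.3** plans graphs of symptoms over time, a baseline-to-EOT comparison for each patient, and one Wilcoxon rank sum test: "The relationship between progression at 6 months by RECIST 1.1 versus the change in rankings from baseline to EOT will be assessed".
- **Protocol Appendix 6 (Data Analysis)** plans descriptive statistics, stream and mean plots, correlations between items, and "a generalized linear mixed model with a covariate for time (weeks or months since registration) and a random intercept term per patient".

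Neither place has an arm term, an arm stratum or a between-arm contrast. Appendix 6 (Compliance) allows the data to be compared with treatment information, but it does not say that they will be or how. The SAP has no PPCB objective, endpoint, method or table shell.

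**The concern.** PPCB is the only patient-reported instrument in the trial, and it is scored weekly under blind. The natural question for such data is whether adding paricalcitol makes patients feel better or worse, and no planned analysis answers it. The single time slope in the Appendix 6 model averages over the two arms and does not estimate their difference. The other exploratory objectives in Protocol 3.3 that concern patient measurements, imaging texture and gut microbiome, do name the arms.

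A second, conditional problem affects the Wilcoxon test. The trial is planned on the premise that arm changes progression. If arm also changes symptoms, the comparison of progressors with non-progressors is partly a comparison of arms. The Protocol offers one possible route: section 1.5 lists "feeling tired, difficulty in thinking clearly, loss of appetite, nausea, vomiting, constipation" among the symptoms of the raised calcium that paricalcitol can cause. The test could then show an association present in neither arm, or hide a real one.

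**Working it through.** **The plan's own figure.** No figure is stated for PPCB. The nearest is the primary power in Protocol 8.2: "A sample size of 12 patients per arm will provide 90% statistical power to detect this difference assuming a one-sided alpha level of 0.05". Enumerating all 13 × 13 outcomes at 1/12 versus 7/12 gives 90.1% for the Pearson test (stated 90%) and 88.8% for the Miettinen-Nurminen score test (stated 89%). The planning rates are therefore read correctly.

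**How strongly arm and progression are linked at those rates.** The expected progression-free patients are 1 control and 7 combination. The expected progressors are 11 and 5.

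- Combination share of progression-free patients: 7/(7+1) = 87.5%.
- Combination share of progressors: 5/(5+11) = 31.25%.
- Difference: 0.875 − 0.3125 = 0.5625.

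An arm effect of d SD on symptom change thus enters the progressor versus non-progressor contrast as about 0.56 × d SD, with no association inside either arm.

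The only maintenance result in the Protocol (1.3: 96% versus 78% progressing) corresponds to 4% versus 22% progression-free. The same calculation gives 0.22/0.26 − 0.78/1.74 = 0.846 − 0.448 = 0.40.

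**False-positive rate of the pooled Wilcoxon test.** The simulation has 12 per arm, progression-free status drawn at the stated rates, normal symptom change with SD 1, no within-arm association, and a two-sided 5% level. The documents give no PPCB SD, so d is an assumed range.

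| Arm shift d (SD) | Pooled, 1/12 vs 7/12 | Stratified by arm, 1/12 vs 7/12 | Pooled, 4% vs 22% |
|---|---|---|---|
| 0 | about 5% | about 5% | – |
| 0.5 | 9% | about 5% | 5% |
| 1.0 | 20% | about 5% | 7% |
| 1.5 | 35% | about 5% | 9% |

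If both arms have a progression-free rate of 1/12, the pooled test rejects in about 3% of trials, so there is no inflation.

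**Masking.** With a real within-arm association of 1.5 SD at the planning rates, pooled power is 86% when arm does not affect symptoms and 41% when symptoms are 1 SD worse on paricalcitol. The stratified (van Elteren) test has about 67–68% power in both cases.

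**What a by-arm comparison can deliver.** With 12 versus 12, a two-sided Wilcoxon test has 20% power at 0.5 SD, 60% at 1 SD and 92% at 1.5 SD. By normal approximation, 80% power needs (1.960 + 0.842) × √(2/12) = 1.14 SD. A 95% interval has a half-width of about 1.960 × √(2/12) = 0.80 SD.

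**How far stratification can be pushed.** With 12 controls at 1/12, P(no progression-free control) = (11/12)^12 = 35% and P(exactly one) = 12 × (1/12) × (11/12)^11 = 38%. In about 74% of trials the control arm has at most one progression-free patient. With exactly one, the smallest two-sided exact p-value in that arm is 2/12 = 0.17.

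**The case against.** The strongest reply is that the analysis matches the objective. The Protocol asks for an association between symptom improvement and progression, and the Wilcoxon test delivers one. Where the sponsor wanted arm comparisons, it wrote them. This stands: the gap is an omission and not an internal contradiction. It does not remove the point, because symptom improvement is also listed as an endpoint in its own right and no analysis relates it to the randomised treatment.

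Several stronger readings are tempting, but the documents do not support them.

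- **That all 24 patients are pooled.** No section says so. Pooling across arms is inferred from the absence of any arm term. The SAP does not impute missing data, and the test needs baseline and EOT scores, so fewer than 24 may be analysed.
- **That the pooled results necessarily absorb a treatment effect.** Distortion needs an arm effect on symptoms and on progression. Protocol 8.2 gives 58% as the level of clinical interest, so the full split is a planning hypothesis. If symptoms improve because progression is prevented, the pooled association is partly a genuine pathway.
- **That dropout of control patients biases the modelled time trend.** A changing mix of arms can move raw mean plots, but the model has a random intercept per patient, which handles constant differences between patients.
- **That paricalcitol's side effects would go unseen.** PPCB follows three disease-related symptoms fixed at baseline, so new side effects register only where they overlap. SAP 7.1 compares toxicity between arms, and its Table 3 shows grade 3 or higher events by arm.
- **That the SAP's silence is telling.** The SAP is titled for clinical endpoints and also leaves out texture and microbiome.

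The direction also matters. If paricalcitol worsens symptoms, virtually all the false positives at the planning rates would show progression-free patients feeling worse, the opposite of the expected association.

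**Conclusion.** The omission holds on the text and depends on no simulation: no specified PPCB analysis contains randomised arm, so the effect of adding paricalcitol on patient-reported symptoms is never estimated. The confounding of the Wilcoxon test is real but conditional. At an assumed 1 SD arm shift with no within-arm association, its false-positive rate is about 20% at 1/12 versus 7/12 and about 7% at 4% versus 22%. There is no inflation if arm does not affect symptoms or does not affect progression. These figures rest on normal symptom changes, complete data in 12 per arm and an SD scale that the documents do not supply. Severity is minor: the endpoint is exploratory, and the primary analysis, sample size, safety and survival analyses are unaffected.

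**What to change.** - **Appendix 6 model:** add randomised arm, arm-by-time and the baseline score. Report the between-arm difference with a 95% CI, labelled exploratory. With 12 per arm this is an estimate and not a decisive test.
- **Plots:** draw the stream and mean plots by arm.
- **Section 8.3.6.3:** keep the pooled Wilcoxon test, which answers the stated objective, and add an arm-stratified (van Elteren) version as a sensitivity analysis. State that it has less power when arm does not affect symptoms (about 67% versus 86% in the example above), and that it rests mostly on the combination arm because few controls are expected to be progression-free. For the same reason, separate tests within each arm are not worth planning.

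The cost is a few lines of text in two places. It needs no new data, visits or patients.

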1.0 BACKGROUND AND RATIONALE

1.1 Overview

Pancreatic cancer continues to be a very lethal disease. It was estimated that in 2016, 53,070 Americans would be diagnosed with pancreatic ductal adenocarcinoma (PDA), and 41,780 would die from the disease. This makes pancreatic cancer the third leading cause of death from cancer in the US.¹

Furthermore it is projected that by 2030, PDA will be the second leading cause of death from cancer in the US. Worldwide, PDA is the twelfth most common cancer, accounting for an estimate of > 300,000 deaths a year.²

Detection of pancreatic cancer has been notoriously very late in the disease and therefore the 5-year survival rate is only 8%. Right now, the only potential cure for pancreatic cancer is surgical resection (if the disease is caught early). However only about 20% of PDA patients are eligible for potentially curable resection and unfortunately most (> 80%) have reoccurrence of their cancer within 2 years of resection, and those reoccurrences are almost universally fatal.^{3,4}

But there is some hope. Recently there are regimens that actually improve survival for patients with advanced stage IV PDA. Conroy and colleagues have developed the Folfirinox regimen, which in a large randomized trial improved survival over gemcitabine as a single agent.⁵ Von Hoff and colleagues developed the nanoparticle albumin (nab) associated paclitaxel plus gemcitabine regimen which improved survival over single agent gemcitabine again in a single randomized trial.⁶ Even more recently Jameson and colleagues have presented a combined regimen of nab-paclitaxel + gemcitabine + cisplatin in a small 24 patient phase Ib/II trial that gave a response rate of 71% with 2 patients having complete response and a median survival of 16+ months.⁷

1.2 A major developing problem in the care of patients with advanced pancreatic cancer

With the greater chance of getting patients with advanced pancreatic cancer into remission, there is a new challenge - keeping the patient in partial or complete remission. The rough parts of trying to keep patients in remission include:

- Cumulative toxicities of the treatment regimens keeping one from continuing the chemotherapeutic regimen.
- Patients get to a maximum amount of tumor shrinkage but that shrinkage often stops after a partial response is reached, e.g. we can see it is likely the patient is no longer benefitting from that regimen or we can see resistance developing.
- Patients get tired of the treatment regimen and want a rest

1.3 Rationale - The reasoning behind a maintenance regimen

It would be wonderful to have an option for patients for when they have achieved the most benefit from the induction regimen they are on if that option:

- a) had a real chance of helping them continue to benefit from treatment
- b) was non-cross resistant and helped improve the patient's chance of non- progression and of improving their survival
- c) caused minimal toxicities
- d) was a very well tolerated regimen and convenient for the patient to take
- e) has a very solid rationale and is worth trying

A real foundation for this rationale for patients who are in best response from their induction chemotherapy is provided by the trial conducted by Reni and colleagues.⁸ In this first phase II randomized maintenance trial, 56 patients who previously had positive optimal response to chemotherapeutic regimens (no progression after 6 months of chemotherapy) were randomized to either observation or treatment with the tyrosine kinase inhibitor (TKI) sunitinib. The results were impressive: 96% of patients had progression after 6 months in the observation arm, while only 78% progressed on sunitinib ($p = 0.04$), 2-year survival was 23% in sunitinib arm versus 7% in the observation arm ($p=0.18$). This important trial demonstrates that a maintenance approach is promising and should be further explored in patients with advanced pancreatic cancer.

However this Reni study did demonstrate that this type of maintenance trial could finally be done in patients with advanced pancreatic cancer put in best response with currently available regimens (and importantly, it could be done in a single institution)!

While immune checkpoint inhibitors have been transformative against multiple types of cancer, patients with advanced pancreatic cancer have been refractory to an immune-oncology approach. The table below details all of the published results from the use of immune checkpoint inhibitors against pancreatic cancer.

Table 1. Immune Checkpoint Inhibitors in PDA

| Target | Agent | n | Responses | | Reference |
|---|-------------------------|----|-----------|--------|-----------------------------------|
| | | | CR | PR | |
| CTLA | Ipilimumab | 27 | 0 | 1-late | Royal et al. 2010 ⁹ |
| PD-L1 | MDX-1105 | 14 | 0 | 0 | Brahmer et al.2012 ¹⁰ |
| PD-L1 | Atezolizumab | 1 | 0 | 0 | Herbst et al. 2014 ¹¹ |
| PD-1 | Nivolumab | | - | | - - |
| PD-1 | Pembrolizumab (MK-3475) | 1 | 0 | 0 | Patnaik et al. 2015 ¹² |
| Note: Possible efficacy in selected patients with MMR deficient tumors. Le et al. NEJM 2016 | | | | | |

There are multiple possible reasons postulated for the real inactivity of the immune-oncology agents (besides the fact that the patients had very advanced pancreatic cancer). These include:

- a) The PDA microenvironment could limit efficacy because it is a very desmoplastic tumor (a physical barrier to therapeutics, driven by tissue resident stellate cells) which reduce intratumor vasculature and delivery of drugs and immune-oncology blockade agents. This desmoplastic reaction has been documented in both the primary pancreatic lesions and in metastatic sites.¹³
- b) The PDA microenvironment is an immunosuppressive cancer cell friendly environment with abundant tumor associated macrophages (TAMs), myeloid-derived suppressor cells (MDSCs) and Tregulatory cells (Tregs). This microenvironment excludes T effector cells which inhibits the patient's antitumor immune response. Therefore the tumor microenvironment is a site of immune privilege for pancreatic cancer cells.

A recent very remarkable finding is that vitamin D receptor (VDR) agonists will sensitize both primary and metastatic pancreatic cancer lesions to PD-1 blockade (in addition to, on its own) making the tumor microenvironment more hostile to the pancreatic cancer cell and more vulnerable to the patient's own immune system. Sherman and colleagues ██████████ ██████████ noted that VDR agonists, particularly those that are synthetic and which cannot be degraded by up-regulated CYP24A1 in the cancer, can reduce tumor fibrosis, can permit drug delivery and can reduce an immunosuppressive environment.¹⁴ Very important is a pilot pre-op SU2C supported clinical trial of nab-paclitaxel plus gemcitabine with the addition of paricalcitol where there were remarkable decreases in extracellular matrix collagen, incredible increases in tumor vascularity, and an enhanced infiltration of CD3 cells. This really set up the question as to whether or not the VDR agonist paricalcitol could improve the activity of an immune checkpoint inhibitor - pembrolizumab.

However we need to have a clinical situation which gives the optimal opportunity for an immune checkpoint inhibitor with or without paricalcitol to work for patients and we think examining the agent in a randomized fashion in a maintenance design is the way to do just that.

